7.3.5 Overall Survival

Overall survival is defined as the duration of time from the start of treatment with LC to the time of death. For the first 2 years after the last dose of LC, patients will be followed for survival every 2 months by telephone call, clinic visit, or medical records. After 2 years have elapsed, patients will be followed every 6 months for survival by telephone call, clinic visit, or medical records.

7.3.6 Progression-free Survival

Progression-free survival is defined as the duration of time from the start of treatment with LC to the time of progression or death, whichever occurs first. For the first 2 years after the last dose of LC, patients will be followed for progression every 2 months by telephone call, clinic visit, or medical records. After 2 years have elapsed, patients will be followed every 6 months for progression by telephone call, clinic visit, or medical records.

7.3.7 Treatment of Overdose

For this study, any dose of LC greater than the assigned dose level for the patient within a 24-hr time period will be considered an overdose.

The Sponsor does not recommend specific treatment for an overdose. There is no antidote to LC. In the event of an overdose, the Investigator or treating physician should:

1. Contact the Medical Monitor immediately.
2. Closely monitor the patient for any AE/SAE and laboratory abnormalities for at least 2 days.

3. Document the quantity of the excess dose as well as the duration of the overdose in the CRF.

Decisions regarding dose interruptions or modifications will be made by the Investigator in consultation with the Medical Monitor based on the clinical evaluation of the patient.

7.4 Pharmacokinetics

Pharmacokinetic parameters are not evaluated in this study.

7.5 Pharmacodynamics

Pharmacodynamic parameters are not evaluated in this study.

7.6 Genetics

Genetics are not evaluated in this study.

7.7 Biomarkers

No specific exploratory or mandatory biomarkers are evaluated in this Phase 1/2 study of LC.

8 STATISTICAL CONSIDERATIONS

8.1 Statistical Hypotheses

There are no formal statistical hypotheses to be tested in this Phase 1/2 study. All statistical analyses will be descriptive in nature. Exact 95% confidence intervals may be generated for select endpoints.

8.2 Sample Size Determination

The study will enroll up to 24 patients in the dose escalation phase. Once the MTD is established, accrual may continue in the dose expansion phase with the objective of studying 6 additional patients at the MTD dose determined in the escalation phase.

8.3 Populations for Analyses

For purposes of analysis, the following populations are defined:

Table 9. Populations for Analysis

Population	Description
Enrolled	All patients who sign the ICF
Evaluable (Escalation Phase)	All escalation patients who receive at least 80% of the planned doses of LC, 80% of planned RT, and 60% of planned TMZ in the first 10 weeks or experience a DLT prior to receiving 10 doses of LC
Efficacy Evaluable (Expansion Phase)	All expansion patients who receive at least 1 dose of LC and have baseline and at least one post-baseline tumor assessment.
Safety	All patients who receive at least 1 dose of LC. Patients will be analyzed according to the dose level they actually receive.

DLT = dose-limiting toxicity; ICF = Informed Consent Form; LC = liposomal curcumin; RT = radiation therapy; TMZ = temozolomide

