3 OBJECTIVES AND ENDPOINTS

Table 3. Objectives and Endpoints

Objective	Endpoint
Primary	

 To determine the MTD/RP2D of LC in combination with RT and TMZ and adjuvant TMZ in newly diagnosed HGG To determine the safety and tolerability of LC infused IV over 3 hr 	
 Number of observed DLTs (as defined in Section 4.1.1)
Secondary	

 To estimate safety and tolerability of LC in combination with standard RT/TMZ and adjuvant TMZ To determine feasibility of weekly LC infusion as defined as patients being able to complete 80% of the planned doses of LC, 80% of RT and 60% of TMZ within the first 10 weeks of treatment To assess efficacy 	
 Safety assessments include SAEs, AEs, findings on physical examination, clinical laboratory findings, and ECGs Proportion of patients at each dose level who receive at least 80% of the planned infusions of LC 80% of RT and 60% of TMZ within the first 10 weeks of treatment OS and PFS at each dose level, PFS based on RANO criteria

AE = adverse event; DLT = dose-limiting toxicity; ECG = electrocardiography; HGG = high-grade glioma; IV = intravenously; LC = liposomal curcumin; MTD = maximum tolerated dose; OS = overall survival; PFS = progression-free survival; RP2D = recommended phase 2 dose; RANO = Response Assessment in Neuro-Oncology; RT = radiation therapy; SAE = serious adverse event; TMZ = temozolomide

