4.1.2 Dose Escalation

Following tumor resection, eligible patients who have signed the Informed Consent Form (ICF) will be assigned a dose of LC.

There will be a maximum of 4 dose levels assessed in this study. The first cohort of patients will start at Dose Level 1 (Table 4). If indicated based on the number of observed DLTs at Dose Level 1, patients may be enrolled in Dose Level -1.

Table 4. Liposomal Curcumin, Radiotherapy, and Temozolomide Dose Escalation Schedule

Dose Level	Dose	
	LC	TMZ
Level -1	240 mg/m ²	75 mg/m ² concurrent RT 150-200 mg/m ² Cycles 1-6 adjuvant
Level 1 (Starting Dose)	300 mg/m ²	
Level 2	350 mg/m ²	
Level 3	400 mg/m ²	

LC = liposomal curcumin; RT = radiotherapy; TMZ = temozolomide

The decision whether a new patient should be assigned to the current dose level or to a higher or lower dose level (escalation or de-escalation) is a function of the number of patients already treated at the current dose level, the number of patients who experienced a DLT at the current dose level, and the number of patients who have neither experienced a DLT nor completed their 10-week DLT evaluation period. The Safety Review Committee (SRC) will oversee dose level decisions throughout the dose escalation phase of the study.

All participating sites are expected to notify the Sponsor when a DLT has occurred.

The study will enroll and treat patients in cohorts of 3 in the dose escalation phase. The first cohort will receive 300 mg/m² (Dose Level 1) of LC weekly. The target DLT risk is 30%. During the assessment window, planned doses will be dropped if the data suggest a $\geq 95\%$ probability that the dose will produce a DLT risk $> 30\%$. Using the proposed time-to-event Bayesian optimal interval (TITE-BOIN) design, enrollment in the escalation phase will stop when 12 patients are assigned to the same dose level or when a total of 24 patients have been treated, whichever happens first.

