7.3 Efficacy Assessments

The efficacy endpoints of this study are OS and PFS.

Patients with measurable enhancing disease will be assessed by the HGG RANO criteria. Patients should be re-evaluated 1 month after the completion of concurrent CRT as well as every 2 cycles (approximately every 8 weeks) with a contrast-enhanced cranial MRI scan. Evidence of PD will be determined as outlined in the RANO criteria below.

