7.3.1 Definition of Evaluable for Efficacy

Enrolled patients are newly diagnosed and there are no restrictions on amount of measurable disease from biopsy, subtotal, or gross total resection. These patients will have their disease evaluated according to the definitions stated below. (Note: Patients who exhibit objective disease progression prior to the end of Cycle 1 will also be considered evaluable.)

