7.3.4 Use of Criteria from Response Assessment in Neuro-Oncology for Assessment of Progression

Progressive disease is defined by *any* of the following:

- a) $\geq 25\%$ increase in sum of the products of perpendicular diameters of enhancing lesions compared to the smallest tumor measurement obtained either at baseline

- (if no decrease) or best response, on stable or increasing doses of corticosteroids. (Stable doses of corticosteroids include patients not on corticosteroids.)
- b) Significant increase in T2-fluid-attenuated inversion recovery (FLAIR) nonenhancing lesion on stable or increasing doses of corticosteroids compared to baseline scan or best response following initiation of therapy, not due to comorbid events (RT, demyelination, ischemic injury, infection, seizures, postoperative changes, or other treatment effects)
 - c) Any new lesion
 - d) Clear clinical deterioration not attributable to other causes apart from the tumor (eg, seizures, medication adverse effects, complications of therapy, cerebrovascular events, infection, etc) or changes in corticosteroid dose. A diagnosis of clinical progression or deterioration may be made at the discretion of the treating physician.
 - e) Failure to return for evaluation due to death or deteriorating condition
 - f) Clear progression of nonmeasurable disease

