8.4.7 Efficacy Analyses

Overall survival will be estimated using the Kaplan-Meier method, with quartile estimates and associated 95% confidence intervals presented. Patients who are alive at the time of analysis will be censored at the last date that they were known to be alive (last study visit if the patient is still on treatment, or last long-term survival assessment where the patient was known to be alive).

Progression-free survival, defined as the time from the day of first study treatment to disease progression or death, whichever occurs first, will be estimated using Kaplan-Meier techniques based on RANO criteria. Patients without evidence of progression will be censored at their last tumor response assessment.

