8.6 Dose Expansion

An expansion cohort will be enrolled after the MTD has been determined in the escalation portion of the study. A maximum of 6 patients will be enrolled in the expansion cohort, dosed at the MTD. Expansion patients will continue to be monitored for safety to ensure that the DLT risk does not exceed 30%. Specifically, if more than 2 patients in the expansion cohort experience a DLT, an ad hoc SRC meeting may be convened to discuss the acceptability of the MTD.

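### The only efficacy population in Table 9 (at most 6 expansion patients, each with a post-baseline assessment) cannot deliver OS and PFS at each dose level, and it drops early deaths that the protocol counts as events

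*Protocol*

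**What the plan says.** Section 7.3 fixes the endpoints: "The efficacy endpoints of this study are OS and PFS". Table 3 (and Table 1 in the synopsis) sets the level at which they are wanted: "OS and PFS at each dose level, PFS based on RANO criteria". Section 8.4 adds that summaries are shown by dose level and over all levels.

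Table 9 in Section 8.3 has a single row for efficacy, labelled as applying to the expansion phase: "All expansion patients who receive at least 1 dose of LC and have baseline and at least one post-baseline tumor assessment". Section 8.6 gives the size of that phase: "A maximum of 6 patients will be enrolled in the expansion cohort, dosed at the MTD". Section 4.1.2 also allows expansion at a lower dose chosen as the RP2D, but that is still one level. On the escalation side, Section 4.1.2 says that "enrollment in the escalation phase will stop when 12 patients are assigned to the same dose level" or when 24 patients have been treated, whichever comes first.

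Section 8.4.7 describes the analysis without naming a population: "Overall survival will be estimated using the Kaplan-Meier method, with quartile estimates and associated 95% confidence intervals presented". Section 8.4.6, by contrast, assigns all safety analyses to the Safety population.

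The event rules are in Section 7.3. OS runs from the start of LC to death (7.3.5). PFS runs to progression or death, whichever is first (7.3.6). Criterion (e) of Section 7.3.4 counts as progression: "Failure to return for evaluation due to death or deteriorating condition". Section 7.3.1, which is headed as the definition of evaluable for efficacy, speaks of enrolled patients with no phase restriction and adds: "Patients who exhibit objective disease progression prior to the end of Cycle 1 will also be considered evaluable".

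**The concern.** The protocol asks for survival and progression results at up to four dose levels, but the only set it labels for efficacy contains one level and at most 6 patients. A SAP author who followed Table 9 literally could not produce the stated endpoint.

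The requirement for a post-baseline assessment raises a second problem. OS needs no scan, and a death before the first scan is a PFS event by definition. Conditioning entry on having an assessment removes such patients and makes the remaining group look better than the treated group. The first scheduled post-baseline MRI is at the start of adjuvant TMZ, about week 10, so there is a real window in which this can happen.

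At stake are the coverage and precision of the OS and PFS estimates and, to a lesser degree, their bias. The analyses are descriptive and no stated decision depends on them, but they are the trial's only efficacy output.

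**Working it through.** **Inputs.** Escalation maximum 24 (Section 8.2); expansion maximum 6 (8.6); up to 30 treated (Section 1.1); at most 12 escalation patients at one dose (4.1.2); mean escalation sizes 15.9, 18.2, 20.7 and 21.6 (Table 11, Scenarios 5, 1, 2 and 3); median survival 14.6 months with RT plus TMZ (Section 2), used only for illustration.

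**Plan's own figure.** 24 + 6 = 30, which agrees with the stated maximum.

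**Coverage.** With E escalation patients, the share of treated patients outside the efficacy set is E/(E + 6):

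- E = 15.9: 15.9/21.9 = 72.6%
- E = 18.2: 18.2/24.2 = 75.2%
- E = 20.7: 20.7/26.7 = 77.5%
- E = 21.6: 21.6/27.6 = 78.3%
- E = 24: 24/30 = 80.0%

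At the expansion dose alone, the set uses 6 of up to 12 + 6 = 18 patients. Up to three of the four dose levels contribute nobody.

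**Precision.** Take the log-log 95% interval for the Kaplan-Meier median with every patient followed to death. The pointwise limits are S^exp(±1.96·√G/|ln S|), where G is the Greenwood sum. Without censoring, after d deaths among n patients, S = (n − d)/n and G = 1/(n − d) − 1/n.

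- n = 6, after the 5th death: S = 1/6, G = 1 − 1/6 = 0.8333, √G/|ln S| = 0.9129/1.7918 = 0.509. The upper limit is (1/6)^exp(−0.999) = 0.517, which exceeds 0.5. After the 6th death S = 0 and the limit is undefined. The interval for the median therefore has no upper end. (The untransformed linear interval does reach one, but only at the 5th of 6 deaths.)
- n = 18: the interval runs from the 5th to the 13th death. Under exponential survival with a 14.6-month median, the median times of these deaths are 6.2 and 24.7 months.
- n = 30: it runs from the 10th to the 21st death, at 8.1 and 24.1 months.

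**Bias from excluding early deaths.** Week 10 is 10/52.18 × 12 = 2.30 months. Let q be the probability of death before then, and f the share of those deaths with no earlier assessment. A share fq is excluded, and the median of the retained group solves S(t) = 0.5(1 − fq). For example, with constant hazard and f = 1: q = 1 − 2^(−2.30/14.6) = 10.3%, so S(t) = 0.448 and t = 16.90 months. All rows below have a true median of 14.6 months:

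| Survival shape | q | f = 1 | f = 0.5 | f = 0.25 |
|---|---|---|---|---|
| Constant hazard | 10.3% | 16.90 | 15.72 | 15.15 |
| Weibull 1.3 | 6.1% | 15.61 | 15.10 | 14.85 |
| Weibull 1.6 | 3.5% | 15.07 | 14.83 | 14.72 |
| Weibull 2.0 | 1.7% | 14.78 | 14.69 | 14.64 |

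The shift in the median is 0.2 to 2.3 months if no early death has an assessment, 0.1 to 1.1 months if half do, and 0.04 to 0.6 months if three quarters do.

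**The case against.** The strongest reply is that the conflict is conditional. Section 8.4.7 does not tie OS or PFS to the efficacy row. Section 8.4 calls its text a high-level summary and lets the SAP prevail, and assigning analyses to populations is normally SAP work. The endpoint tables and the by-dose-level rule already point to a wider set, and the OS censoring rule needs no scan. This is true as far as it goes. But the objection here is to a row the protocol did write, not to detail it left out. A SAP that followed the row would miss the endpoint; one that did not would have to set aside the protocol's only efficacy set.

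It can also be said that the set was meant for a summary of tumor response, since Section 7.3.2 mentions objective response. That is possible, but response is not an endpoint in Table 3 or Section 7.3.

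Several narrower points stand:

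- Section 7.3.1 keeps patients with objective progression, which implies an assessment. It therefore conflicts with the phase restriction, not with the assessment requirement.
- Table 9 says tumor assessment rather than MRI, and discretionary and End of Treatment scans will keep some early failures in the set.
- Grade III and IDH-mutant patients are eligible, so the 14.6-month median may overstate early deaths. With constant hazard and medians of 20 to 24 months, q falls to about 8% to 6%.
- The fix does not make each level precise. In Scenario 2 of Table 11, three of the four levels average 0.233 × 20.7 = 4.8, 0.229 × 20.7 = 4.7 and 0.041 × 20.7 = 0.8 patients. Such levels would still have no upper limit for the median unless the expansion were added there. The gain in precision is at the expansion dose and in the pooled summary.

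**Conclusion.** The concern holds. As written, the only efficacy population in Table 9 cannot produce OS and PFS at each dose level, and its assessment requirement is at odds with the protocol's own event definitions. If it is used, 73% to 80% of treated patients are left out, and at the expansion dose up to 12 of 18. The median then rests on 6 patients or fewer, with no upper confidence limit by the log-log method.

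The coverage figures come directly from the protocol's numbers. The interval times assume exponential survival, a 14.6-month median and complete follow-up. The bias is upward and probably modest. Its size depends on the assumed hazard shape and on how many early deaths have an earlier assessment, neither of which the protocol gives.

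This should be fixed, but it concerns a descriptive secondary endpoint and nothing is irrecoverable.

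**What to change.** State in Section 8.4.7 that OS and PFS are analysed in all patients who receive at least one dose of LC (the existing Safety population), from both phases, by dose level received and overall. For these two endpoints, remove the expansion restriction and the post-baseline assessment requirement from the efficacy row of Table 9. Reconcile that row with Sections 7.3.1 and 7.3.4(e), so that death or deterioration before the first scan counts as an event. If an assessment-based set is still wanted, keep it as supportive and say what it is for.

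The cost is one table row and one sentence. Survival and progression follow-up is already planned for treated patients in both phases, so no extra data are needed. The SAP was not available for this review and should be aligned with the corrected text.

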8.4 Statistical Analyses

Summaries will be presented by dose level and over all dose levels. The summaries will present descriptive statistics (mean, standard deviation, median, minimum, and maximum) for continuous variables and frequencies and percentages for categorical variables.

Exact 95% confidence intervals may be generated for select endpoints. All data will be included in patient listings.

The statistical analysis plan (SAP) will be developed and finalized prior to database lock. The SAP will provide additional details on the statistical analyses, including procedures for accounting for missing data and outliers.

A high-level summary of the planned statistical analyses of the primary and secondary endpoints is presented below. If there are any differences between the analyses described in the protocol and the SAP, the SAP will prevail.

8.4.1 *Disposition and Demographics*

Summaries and descriptive statistics of demographic and baseline characteristics will be provided. Descriptive statistics for age, gender, race, ethnicity, height, weight, and body mass index will be generated.

Study and treatment completion status will be summarized, with reasons for premature discontinuation of treatment and of the study presented.

A summary of the number of patients in each study population will also be generated.

8.4.2 *Baseline Characteristics and Protocol Deviations*

Baseline characteristics and number of protocol deviations (any, minor and major) will be summarized overall and by dose group.

8.4.3 *Drug Exposure*

Drug exposure will be summarized based on the number of doses received for each study treatment (LC, CRT and RT) as well as the total dose received (separately for LC, CRT and RT), the number of cycles of CRT and the duration of treatment for LC, CRT and RT. Dose interruptions and adjustments will also be summarized.

8.4.4 *Karnofsky Performance Scale*

Scores on the KPS will be summarized at each assessment. Shift tables from baseline to maximum observed KPS score may also be generated.

8.4.5 *Concomitant Medications*

Concomitant medications will be summarized using the World Health Organization Drug Dictionary (WHODrug). Prior concomitant medications (medications used prior to study enrollment and stopped prior to the first study drug administration) will be summarized separately.

8.4.6 *Safety Analyses*

All safety analyses will be performed on the Safety Population. Safety analyses will be presented by dose level and overall. Separate safety analyses for the escalation and expansion phases may be generated for patients treated at the MTD for select safety endpoints.

Safety endpoints include DLTs, AEs, changes in laboratory values, ECGs, and changes in vital signs. All AE terms will be coded using MedDRA preferred term and system organ class.

The proportion of patients experiencing at least 1 DLT as well as the number of DLTs observed will be summarized using frequency table techniques; Exact 95% confidence intervals may be generated. Adverse events occurring after the first study intervention will be summarized as follows: all AEs, SAEs, AEs related to study drug, AEs by severity, AEs by grade using CTCAE, and AEs leading to death.

Laboratory and vital sign data will be summarized as continuous variables by dose level and time point. Changes from baseline will be presented along with observed value at each time point. Select laboratory parameters may be graded using CTCAE. Grades for these lab parameters will be summarized in shift tables comparing the baseline grade to the maximum observed post-baseline grade.

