5.1 Inclusion Criteria

Women and members of minority groups will be actively recruited. No exclusion to this study will be based on gender, race, or ethnicity.

Patients are eligible to be included in the study only if all of the following criteria apply:

1. Capable of giving signed informed consent as described in [Section 9.1.3](#) (Appendix 1) that includes compliance with the requirements and restrictions listed in the ICF and in this protocol.
2. ≥ 18 years of age
3. Histologically confirmed HGG (WHO grade III or IV, including GBM, astrocytoma, gliosarcoma, *H3K27M* mutant diffuse midline glioma). Patients with methylated or unmethylated O(6)-methylguanine-DNA methyltransferase (MGMT) promoter are eligible, as are IDH WT and mutant patients as long as the treatment plan is for combined RT/TMZ. The neuropathologic diagnosis of HGG will be made at the respective institution. If any question arises regarding the accuracy of the neuropathologic diagnosis, slides (and pathological blocks, if necessary) will be centrally reviewed.
4. Planning standard therapy with TMZ and RT for 6 weeks
5. Karnofsky Performance Scale (KPS) $\geq 60\%$ ([Section 9.6](#) [Appendix 6])
6. Adequate organ and marrow function defined as:

Hgb	> 9 g/dL
ANC	$\geq 1500/\mu\text{L}$
Platelet count	$\geq 100,000/\mu\text{L}$
Total bilirubin	≤ 1.5 * institutional ULN
AST and ALT	≤ 3 * institutional ULN
Creatinine	≤ 1.5 * institutional ULN

OR

Estimated glomerular filtration rate (eGFR)	≥ 60 mL/min/1.73 m ² unless data exist supporting safe use at lower values of renal function, but eGFR must be ≥ 30 mL/min/1.73 m ²
---	---

7. Patients with human immunodeficiency virus (HIV) who are on effective antiretroviral therapy are eligible if the viral load was assessed as undetectable within 6 months prior to baseline.
8. Women: WOCBP must agree to use adequate contraception (hormonal or barrier method of birth control or abstinence) prior to study entry and for the duration of study participation.

Men: must agree to use adequate contraception prior to study entry, for the duration of study participation, and for 4 months after completion of LC administration.

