9.6 Appendix 6: Karnofsky Performance Scale

Table 20. Karnofsky Performance Scale

Percent	Description
100	Normal, no complaints, no evidence of disease
90	Able to carry on normal activity; minor signs or symptoms of disease
80	Normal activity with effort; some signs or symptoms of disease
70	Cares for self; unable to carry on normal activity or to do active work
60	Requires occasional assistance, but is able to care for most of his/her needs
50	Requires considerable assistance and frequent medical care
40	Disabled, requires special care and assistance
30	Severely disabled, hospitalization indicated. Death not imminent
20	Very sick, hospitalization indicated. Death not imminent
10	Moribund, fatal processes progressing rapidly
0	Dead

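### The optional KPS shift table in Section 8.4.4 compares baseline with the patient's best score, so it understates functional decline

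*Protocol*

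**What the plan says.** Section 8.4.4 makes two statements about KPS. The first is a firm commitment: "Scores on the KPS will be summarized at each assessment". The second is optional: "Shift tables from baseline to maximum observed KPS score may also be generated". The second does not say whether the maximum is taken over post-baseline scores only or over all scores including baseline.

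Table 20 in Appendix 6 fixes the direction of the scale. A score of 100 is described as "Normal, no complaints, no evidence of disease", a score of 10 as "Moribund, fatal processes progressing rapidly", and 0 is dead. A higher score is better.

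Section 8.4.6 plans a similar display for laboratory parameters graded by CTCAE: "shift tables comparing the baseline grade to the maximum observed post-baseline grade". There a higher grade is worse.

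Section 8.4 also states: "All data will be included in patient listings". The protocol plans no shift to the lowest or worst KPS score.

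**The concern.** Among safety displays, a shift table is normally there to show how far each patient moved in the unfavourable direction. For CTCAE grades the maximum does that. For KPS the maximum does the opposite: it picks each patient's best moment and sets it against baseline.

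Safety and tolerability are primary and secondary objectives (Section 3, Table 3). Entry requires a KPS of at least 60% (Section 5.1), so every patient has room to fall. Summaries are by dose level (Section 8.4), with up to 24 escalation patients and 6 expansion patients (Section 8.2). Dose groups will be small, and a few understated declines could change how a dose level looks in this table.

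**Working it through.** The protocol gives no figure to reproduce. The check applies the stated rule to the stated scale.

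**Notation.** Let b be the baseline score and p1, ..., pk the later scores. A negative shift means worsening.

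**Reading 1: baseline counts in the maximum.** Shift = max(b, p1, ..., pk) − b. This is never below 0, so no patient can fall in a worsening cell, whatever happens later.

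**Reading 2: post-baseline scores only.** Shift = max(p1, ..., pk) − b. This is below 0 only if every later score is below b. Its size is then the smallest of the drops b − p1, ..., b − pk. One later score at or above baseline is enough for that patient to be shown as unchanged or improved.

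**Worst-score rule.** Shift = min(p1, ..., pk) − b.

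Four invented courses, for illustration only:

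| Baseline | Later scores | Reading 1 | Reading 2 | Worst score |
|---|---|---|---|---|
| 90 | 90, 80, 60, 40 | 90 − 90 = 0 | 90 − 90 = 0 | 40 − 90 = −50 |
| 80 | 90, 70, 50 | 90 − 80 = +10 | 90 − 80 = +10 | 50 − 80 = −30 |
| 90 | 80, 70, 60 | 90 − 90 = 0 | 80 − 90 = −10 | 60 − 90 = −30 |
| 70 | 70, 80, 80 | 80 − 70 = +10 | 80 − 70 = +10 | 70 − 70 = 0 |

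The second patient loses 30 points and is shown as improved under either reading. The third is the case where Reading 2 does show a decline, but of 10 points rather than 30. The fourth shows what the worst-score rule gives up: a patient who only improves appears as unchanged.

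**Illustrative simulation of Reading 2.** All inputs are assumptions, not from the protocol: baseline drawn evenly from 60 to 100 in tens; a change of −10, 0 or +10 at each visit; a chance of decline of 20%, 30% or 40% per visit; a chance of gain of 10%; 4 or 8 visits; 200,000 patients per setting. Among patients whose score fell at least 20 points below baseline at some visit, the share shown with any worsening was:

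| Chance of decline per visit | 4 visits | 8 visits |
|---|---|---|
| 20% | 55.1% | 30.6% |
| 30% | 57.7% | 34.6% |
| 40% | 60.4% | 39.4% |

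So about 31% to 60% appeared as worse and the rest as unchanged or improved. None appeared with a drop of 20 points or more. That zero follows from the assumed step size: the first later score can be at most 10 points below baseline, so the maximum cannot be lower than that. With larger steps, larger drops could appear. The simulation shows the direction of the distortion and is not a forecast for this trial.

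**The case against.** The strongest case on the other side concerns reach, not direction.

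- **A reader might infer that deterioration can never appear, or that 0% of patients can be shown as worse.** The protocol does not support that without qualification. It holds only under Reading 1, and Section 8.4.4 does not say that baseline counts. A table running from baseline to something else is ordinarily read as baseline against later values, and then some decliners do appear, with a reduced drop. This objection stands.
- **A reader might infer that the analysis as a whole hides loss of function.** It does not. The by-assessment summary is a firm commitment. Section 8.4 specifies mean, standard deviation, median, minimum and maximum for continuous variables, and frequencies for categorical ones. A fall from 90 to 40 would show at that visit and in the listings. This also stands, although by-assessment summaries do not give each patient's worst change from baseline, which a shift table is well suited to show.
- **KPS is not a named safety endpoint.** It is absent from the safety assessments in Table 3 and from the endpoints in Section 8.4.6. Some functional decline is captured elsewhere, as neurological dose-limiting toxicity (Section 4.1.1) or as clinical deterioration under the progression criteria (Section 7.3.4). This stands and keeps the point minor.
- **A best-score shift may be deliberate, to show improvement.** That is a legitimate display, and the protocol states no purpose for the table. That the wording was carried over from the laboratory rule is plausible but cannot be shown; the laboratory sentence has a post-baseline restriction that the KPS sentence lacks. Even if deliberate, a best-score shift as the only KPS shift leaves the unfavourable direction uncovered.
- **The table is optional and the SAP prevails over the protocol.** True, but the protocol is not silent here. It names a comparator, and an SAP author who follows it would build a table that understates harm.

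**Conclusion.** The rule is wrong as written, and the consequence is minor. On the protocol's own scale, the KPS shift table compares baseline with the best score and so understates decline under either reading: completely if baseline counts in the maximum, and partly if it does not. This rests only on Section 8.4.4 and Table 20.

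How many patients would be affected cannot be derived from the protocol, because it depends on their actual KPS courses; the simulated 31% to 60% depends on its assumed inputs. No dose decision or stopping rule uses the table, and Section 8.1 states: "There are no formal statistical hypotheses to be tested in this Phase 1/2 study". The conclusion does not extend to the by-assessment KPS summaries or the listings, which still show decline.

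**What to change.** In Section 8.4.4, replace the maximum observed KPS score with the *minimum (worst) post-baseline KPS score* as the value to which the shift is made. The post-baseline restriction matters as much as the change of direction, because it settles whether baseline itself counts. If improvement is also of interest, keep a shift to the best post-baseline score as an additional, separately labelled table. The SAP should carry the same definition.

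The cost is a few words. No new data, visits or patients are needed, and clinical management is not affected.
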